### **9.2. Sample Size Considerations**

The following was performed for each of the proposed LAR primary endpoints:

[figure not shown]
- Success criteria: declare endpoint success if the posterior probability of any treatment attenuation exceeds 0.7.
- The probability of declaring a success has been computed for a range of true percent attenuations and sample sizes (n per arm equal allocation). To make the figures easier to interpret the “nuisance” parameters of the placebo response and the standard deviation have been accounted for as follows:
- Eight previous GSK BAC studies (Crossover design) have been re-analysed to obtain estimates of the average placebo response and the associated estimate of residual variability applicable to the proposed Parallel Group design.
- These estimates were combined in a random effects meta-analysis to obtain posterior distributions for the underlying parameter values (placebo average response, residual variability (for an individual subject) and a between study variance component). The future placebo response was computed as the sum of random draws from the posterior distributions of the placebo average response parameter and a normal distribution with mean zero and variance equal to the between study variance parameter. The future GSK2245035 response was derived using the simulation scenario’s true percentage attenuation. A pooled sample variance value was generated using a Chi-Square distribution with degrees of freedom appropriate to the simulation scenario and a sampled variance from the meta-analysis posterior distribution. Those numbers were entered into the standard formulae for power curves. Repeating this process 10,000 times and taking the median of the resulting power values constructs “Assurance” operational characteristics for the combination of true percent attenuation and sample size under evaluation.

- These assurance operational curves have been summarised graphically. The x-axis is a hypothetical true drug effect that is assumed to be known for experimental design purposes.
- The simulations can also be used to compute the minimum observed percentage attenuations that would result in a successful study outcome. The median (of the 10,000 simulations) have been derived for a variety of sample sizes and success criteria (probability thresholds 0.7, 0.75, 0.8, 0.85, 0.95) and displayed graphically. The y-axis is the observed effect from the study data.

[figure not shown]

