- Active: Sample Mean Vector $\begin{bmatrix} \bar{x}_1 & \bar{x}_2 \end{bmatrix}_{Act}$ Sample VCV $\begin{bmatrix} S_{WM}^2 & S_{WM}S_{Min} \\ S_{WM}S_{Min} & S_{Min}^2 \end{bmatrix}_{Act}$

Interim Analyses to estimate end of study success
--

- In the statistical model fitted to the WM endpoint the priors are:

$$\hat{\mu}_{P,WM} \sim N\left(\bar{x}_{1,Pbo}^{WM}, \frac{S_{WM,Pbo}^2}{Nrem_{Pbo}}\right), \quad \hat{\mu}_{A,WM} \sim N\left(\bar{x}_{1,Act}^{WM}, \frac{S_{WM,Act}^2}{Nrem_{Act}}\right)$$

- In the statistical model fitted to the Min endpoint the priors are

$$\hat{\mu}_{P,Min} \sim N\left(\bar{x}_{2,Pbo}^{Min}, \frac{S_{Min,Pbo}^2}{Nrem_{Pbo}}\right), \quad \hat{\mu}_{A,Min} \sim N\left(\bar{x}_{2,Act}^{Min}, \frac{S_{Min,Act}^2}{Nrem_{Act}}\right)$$

Step 3: Fit model and flag success or failure
--

- To facilitate easy use of the prior distributions a re-parameterized version of Primary analysis Model M3 can be used (Intercept term removed and the zero constraint on the 2nd treatment level removed).
- Separate models will be fitted to each of the endpoints (WM and Min)
- If the posterior probability that $\hat{\mu}_P < \hat{\mu}_A$ exceeds 0.7 (using the informative prior from the ith MCMC iteration) then the ith MCMC iteration is flagged as resulting in a successful end of study result.
- The overall probability of success is the number of successful MCMC iterations / total number of MCMC iterations

Technical details for deriving the individual tables contributing to [Table 2](#)

To determine the probability of success in the presence of non-LAR responders simulations were performed for each possible combination of number of available placebo subjects (n) and number showing no LAR response (r) using the AZ point estimates as the true percentage attenuation (separate procedure for each of the primary endpoints):

Let K represent the number of subjects per arm to be evaluated with each value of K producing a different table and K ranging from 21 to 30 by 1.

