7.1.2 Planned Efficacy Statistical Analyses

Primary Statistical Analyses
Endpoint(s)

 • LAR: minimum <change from saline baseline> FEV₁ between 4-10 hours following allergen challenge 1 week after treatment i.e. FUV1. • LAR: weighted mean of <change from saline baseline> FEV₁ between 4-10 hours following allergen challenge 1 week after treatment i.e. FUV1. 
Note: Text in <> added for clarity, since the wording in the protocol and objectives is familiar to clinical experts in the field, but may be confusing given there are also absolute FEV1 values measured at those times too.
 
 • The “raw” data (replicate (absolute) FEV1 values transcribed into the eCRF) require processing before the Primary analysis. Each planned timepoint may be associated with replicate FEV1 values, which need to be condensed down into a single value (giving a single FEV1 value per timepoint per subject; the timepoints determine how the data are condensed, i.e. some timepoints use the minimum of the replicates others use the maximum). In addition the Screening Visit 2 Incremental BAC challenge may also contain additional FEV1 values relating to the selection procedure for the bolus BAC concentration. Such FEV1 values are not used in the statistical analyses (subjects may differ in the amounts of additional FEV1 data to be excluded). Once the single time profile of absolute FEV1 values is available per subject the Saline baseline is subtracted from each to leave a time profile of change from saline baseline FEV1 values. The minimum and weighted means endpoints are derived from this change from saline baseline time profile. Further details are given in Section 11.5.4. • Any transformation of a response variable is also expected to be applied to the corresponding baseline variable. Final decisions on transformations will be based on the observed data and model diagnostics • Any observations with missing model covariates (e.g. baseline) would be excluded from the model fitting process (i.e. also excluding the record from any centering of covariates)
Model Specification

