
 A scatterplot of each subject's two derived primary endpoints (each endpoint is an axis) – with appropriate identification of subjects belonging to the four distinct treatment & allergen exposure combinations. Include i) the (overall) Pearson correlation coefficient and optionally ii) corresponding density estimates for each combination and axis as plot margin panels As an informal check the weakly informative prior on the variance component of the centre effect may be replaced by a non-informative prior and the treatment estimates compared, provided both models converge, to confirm the prior is not more informative than was intended (outputs from this check do not need to be formally reported) Informative priors based on AZ published data/effect sizes may be explored for the treatment terms. Priors that need to be modified in models M1, M2 and M3 are indicated below (Priors for WM LAR endpoint only, and analysis would only be required for PP population): 			
Type	Name (#Levels)	Parameters	Prior(s)
Fixed Categorical	Intercept (1)	#1 Intercept	N (-0.7081, Var=0.4472^2 / 26)
	Treatment (2)	#1 Placebo	N (-0.2619, Var=0.4472^2 * (1/25 – 1/26))
		#2 20ng	n/a (constraint = 0)

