8.4.3.3 Multivariate Statistical Analysis Strategy

The following is a top level description of the (exploratory) analysis strategy; further refinements may be required once the number of endpoints and their distribution are known (i.e. data driven modifications to the planned analysis may be made during study reporting). Please consult the GSK study statistician for further details if required. Further details of the methodology used would be included in the CPSR.

- Whenever possible, to preserve the maximum amount of information contained within them, continuous variables should not be dichotomised.
- Imputed biomarker responses would be used in this analysis (e.g. responses below LLQ would be assigned $\frac{1}{2}$ LLQ).
- Missing data / covariate values: Given the exploratory nature and relatively small number of subjects strong simplifying assumptions will be made. A missing at random assumption will be made for response variables. Initially for simplicity, covariates that are missing would be replaced with the corresponding treatment arm mean. A possible extension may use multiple imputation methodology to sample 5 sets of complete cases (via MCMC sampling methodology since the missingness patterns are not expected to be monotonic), analyse each of the 5 datasets separately and combine them using Rubin’s rules (e.g. via SAS PROC MI and PROC MIANALYZE). This extension would be considered if the number of missing covariates is deemed large by the GSK study statistician.
- Two approaches would be attempted each aiming to explore the magnitude and duration of any GSK2245035 drug related as assessed using a range of endpoints. If the observed data do not permit their use or their assumptions are unlikely to be valid these methods may not be attempted.

- Profile regression (via the PReMiM R package) – see [Liverani \(2015\)](#).
 - Response variable: BAC LAR outcomes (continuous Primary endpoint(s)). Separate modelling for each of the two primary endpoints
 - For simplicity, the repeated measures aspect will be ignored and data from each visit for an individual will be assumed to be independent.
 - For display purposes the endpoints will be grouped by (biomarker) functional category listed in [Table 13](#); with the option to explore the inclusion of other variables via additional functional categories; for example but not limited to FeNo and diary card WM TNSS value(s).

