 - If necessary biomarkers from a functional category may be omitted if there appears to be a larger amount of multicollinearity.
 - Log transformed data used, individual variables may be standardised prior to model fitting.
 - Treatment and visit information would not be provided to the model fitting process.
 - A desirable outcome is if the number of clusters roughly matches the treatment and visit combinations (approximately 6) and/or that individuals from the same treatment arms are consistently clustering together. Also it is desirable that the expected response associated with any “GSK2245035 clusters” is lower than “placebo clusters”.
- Unsupervised clustering of individuals and visits followed by Canonical Correspondence analysis / Principal co-ordinates analysis to identify patterns when grouping results by treatment and visit – See [Valles \(2014\)](#)
 - The strategy described in [Valles \(2014\)](#) would be modified to reflect the continuous data in this study (rather than binary presence/absence in their data).
 - Each variable may be standardised prior to model fitting.
 - For each subject and visit combination their associated two primary response variables and the potential set of biomarkers described above for profile regression (plus the option to include other variables, for example but not limited to FeNo and diary card WM TNSS value(s)) would be put through an unsupervised clustering algorithm and the resulting dendrogram would also identify the timepoint and treatment associated with each sample

as well as colour coding by the standardised absolute values (see Fig 3 of the [Valles](#) (2014) paper).

- Additionally Canonical Correspondence analysis / Principal coordinates analysis would be used to explore patterns in samples belonging to the same treatment and visit. As in Fig 4 of [Valles](#) (2014) convex hulls may be drawn around the data points relating to samples from each treatment and timepoint combination and the areas of overlap determined and compared. Separately for each treatment arm and taking its respective Screening visit convex hull area as a reference, the area of overlap from the follow up visits would be expressed as a percentage of screening. Additionally and separately for each visit the convex hull area of GSK2245035 would be expressed relative to the Placebo convex hull area. The relative changes in these areas can potentially inform on magnitude and duration of treatment effects.

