11.4.2.2 Derivations and Handling of Missing Baseline Data

Definition	Reporting Details
Change from Saline ¹	=Highest Challenge Value – Highest Saline Value
% Change from Saline ¹	= $100 \times [(Highest\ Challenge\ Value - Highest\ Saline\ Value) / Highest\ Saline\ Value]$
% Attenuation of Reference Response	= $100 \times [1 - (Test\ Mean / Reference\ Mean)]$
Change from Baseline	= Post-Dose Visit Value – Baseline
% Change from Baseline	= $100 \times [(Post-Dose\ Visit\ Value - Baseline) / Baseline]$
Maximum Change from Baseline	= Calculate the change from baseline at each given time point and determine the maximum change

NOTES :

- Unless otherwise specified, the baseline definitions specified in Section 11.4.2.1 Baseline Definitions will be used for derivations for endpoints / parameters and indicated on summaries and listings.
- Unless otherwise stated, if baseline data is missing no derivation will be performed and will be set to missing.
- The baseline definition should be footnoted on all change from baseline displays.

1. Example of calculations of Change and % Change from Saline in the BAC:

Challenge concentration (squ/mL)	Planned relative time	FEV1 (L)	FEV1 Change		
			Max FEV1 (L)	from Max Saline (L)	(%)
45250	Saline	2 M	3.79	4.02	
		3 M	4.02		
		4 M	3.83		
		5 M	4.11	4.11	2.2
		10 M	4.08	4.08	0.06 1.5
		15 M	3.86	3.86	-0.16 -4.0
		20 M	3.97	3.97	-0.05 -1.2
		30 M	4.16	4.16	0.14 3.5
		45 M	4.12	4.12	0.10 2.5
	1 H-READ 1		4.14	4.14	0.12 3.0
	1 H-READ 2		3.76		

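### In the exploratory profile regression (SAP 8.4.3.3), the stated desirable direction for the late asthmatic response is reversed relative to the scale of the endpoint

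*SAP*

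**What the plan says.** SAP 8.4.3.3 describes two exploratory multivariate approaches. The first is a profile regression, fitted separately for each primary endpoint. The outcome is given as "Response variable: BAC LAR outcomes (continuous Primary endpoint(s". Treatment and visit are withheld from the fit, and clusters are then examined to see whether they line up with treatment arms. Two desirable findings are listed. One is that clusters roughly match the treatment and visit combinations, or group subjects from the same arm. The other concerns direction: "it is desirable that the expected response associated with any “GSK2245035 clusters” is lower than “placebo clusters".

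The scale of the outcome is fixed elsewhere in the SAP:

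- SAP 7.1.2: "Once the single time profile of absolute FEV1 values is available per subject the Saline baseline is subtracted from each", and then "The minimum and weighted means endpoints are derived from this change from saline baseline time profile".
- SAP 11.4.2.2 defines change from saline as "Highest Challenge Value – Highest Saline Value".

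The favourable direction on that scale is also given. In SAP 3.1, Step 3, a simulated study is flagged as successful under the condition "If the posterior probability that $\hat{\mu}_P < \hat{\mu}_A$ exceeds 0.7", where P is placebo and A is active.

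**The concern.** Challenge minus saline is negative when FEV1 falls. On that scale a lower expected response is a deeper late fall in FEV1, which is a worse outcome. The sentence in 8.4.3.3 therefore calls the unfavourable direction desirable and disagrees with SAP 3.1 and 7.1.2 on the same endpoints.

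What is at stake is how the exploratory output is read. Because treatment is not supplied to the model, clusters are labelled as active or placebo only afterwards. In 8.4.3.3 this sentence is the only stated link between a profile-regression cluster labelled active and a benefit of the drug. The profile-regression table, figure and listing (Table 5.27, Figure 5.70 and Listing 100 in SAP 11.13) have no example shell that could supply the direction. Followed literally, the sentence would make the exploratory reading contradict the primary analysis of the same data.

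**Working it through.** **Inputs**

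- Informative prior for the intercept, WM LAR (SAP 7.1.2): "N (-0.7081, Var=0.4472^2 / 26"). The 20 ng effect is constrained to zero, so the intercept is the active mean, -0.7081.
- Informative prior mean for the placebo term (same table): -0.2619.
- Percentage attenuation (SAP 7.1.2): 100 × (1 − Intercept / (Intercept + Treatment[#1])).
- Assumed effects (SAP 3.1 and 7.1.2): 27% for WM LAR and 18% for minimum LAR.
- Historical placebo means (protocol Table 2): minimum LAR -1.4484 to -0.7309; WM LAR -0.9817 to -0.3749. All 16 values are negative.
- Values assigned to a subject with no LAR (protocol 9.3.2, SAP 3.1): -0.45 (minimum) and -0.20 (WM).

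**Step 1: reproduce the plan's own figure**

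Placebo mean = -0.7081 + (-0.2619) = -0.9700.

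Attenuation = 100 × (1 − (-0.7081)/(-0.9700)) = 100 × (1 − 0.730) = 27.0%.

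This matches the stated 27%. The SAP's priors therefore encode the assumed benefit as an active mean 0.2619 L **above** placebo.

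**Step 2: apply both directions to a range of true effects on WM LAR**

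Active mean = -0.970 × (1 − attenuation), with worsening entered as negative attenuation.

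| True effect | Active mean (L) | Active lower than placebo (8.4.3.3)? | Placebo mean below active mean (3.1)? |
|---|---|---|---|
| 27% attenuation | -0.708 | No | Yes |
| 10% attenuation | -0.873 | No | Yes |
| None | -0.970 | No | No |
| 10% worsening | -1.067 | Yes | No |
| 27% worsening | -1.232 | Yes | No |

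Full attenuation gives 0, which also fails the 8.4.3.3 direction. The two sections disagree for every non-zero effect in the table.

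**Step 3: check that this does not depend on the priors**

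Plain means of the Table 2 placebo responses are -1.050 (minimum) and -0.656 (WM). The assumed effects give:

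- minimum: -1.050 × 0.82 = -0.861, which is higher than placebo by 0.189 L;
- WM: -0.656 × 0.73 = -0.479, which is higher by 0.177 L.

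The values assigned to subjects with no LAR, -0.45 and -0.20, lie above all eight historical placebo means for their endpoint (the highest are -0.7309 and -0.3749). Less late response means a higher value.

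**Step 4: check whether pre-processing removes the problem**

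SAP 8.4.3.3 says that log-transformed data are used and that variables may be standardised. Standardising subtracts a constant and divides by a positive one, so the order is kept. A negative value has no logarithm, so the log line cannot apply to the signed LAR response as it stands. No sign reversal is stated.

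**The case against.** The strongest defence is that *response* here means the size of the asthmatic response. The SAP does write that way in places. Section 7.1.2 treats a treatment reduction and a percentage attenuation as the same thing, and Table 15 in 8.4.3.2 speaks of attenuating the LAR response. In that vocabulary a lower response is a smaller LAR, which is benefit. The log line can be taken the same way: if the response were sign-reversed before logging, *lower* would be correct.

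This may well be what was intended, and it affects how the correction should be worded. It does not settle the text. Section 8.4.3.3 names the continuous primary endpoint as the response, and no sentence there reverses its sign or defines it as the size of the fall. Where 7.1.2 speaks of a reduction it adds the attenuation gloss at once; 8.4.3.3 has no such gloss.

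The second defence is that little hangs on the sentence. The section is a top-level, exploratory strategy that allows data-driven changes and may not be carried out at all. Readers are referred to the study statistician, and the correct direction is available elsewhere in the SAP. All of this stands, and it limits the weight of the point. Freedom to adapt the analysis after seeing the data is, however, a reason for having the pre-stated direction right.

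**Conclusion.** The direction in SAP 8.4.3.3 is wrong as written. On the signed change-from-saline scale, the assumed 27% benefit in WM LAR (-0.708 against -0.970) fails it and an equal worsening (-1.232) meets it. This rests on reading the response as the endpoint defined in SAP 7.1.2, with no unstated sign change. The intent was probably a smaller LAR.

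Two stronger readings are tempting, and the documents do not support them.

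- *That the SAP contains a rule under which a harmful drug would be declared successful.* The sentence states what is desirable. It carries no threshold, probability or decision. The criterion that does carry one is in protocol 9.2, "declare endpoint success if the posterior probability of any treatment attenuation exceeds 0.7", and it is framed as attenuation, in the right direction. The primary analysis, the interim prediction and the fit of the profile regression itself are the same whichever word is printed.
- *That one can give the chance of the sentence being met under benefit or harm.* That would need clusters to be the two arms at one visit. The planned model is blind to treatment, treats an individual's visits as independent, and hopes for about six clusters, so a two-arm calculation would not describe it.

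The point is therefore a definite error of wording on the primary endpoint's scale, confined to the interpretation of an exploratory analysis.

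**What to change.** Make one of two changes in SAP 8.4.3.3:

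1. replace *lower* with *higher (less negative change from saline, i.e. an attenuated LAR)*; or
2. define the modelled response as the size of the fall, with the sign reversed, and keep *lower*.

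The first needs no new derivation and agrees directly with SAP 3.1 and 7.1.2. With either, add a sentence saying that the log transformation applies to the biomarkers and not to the signed LAR response. Changing the one word alone would leave the modelled scale unclear.

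The cost is a sentence or two in the SAP. No data collection changes. Option 1 needs no programming; option 2 needs a sign change in the input dataset.

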- Desirable outcomes would be distinct clusters by treatment arm(s) and lasting changes (across FUV1, FUV2 and FUV3) in convex hull areas on active that are not observed on the placebo.

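### In the exploratory ordination analysis, the hull-area criteria measure spread and subject count, not a shift, so they are a poor guide to the size and duration of a drug effect

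*SAP*

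**What the plan says.** SAP 8.4.3.3 describes two exploratory multivariate approaches, both aimed at the magnitude and duration of any drug effect. The second clusters subject-visits on the two LAR endpoints and the biomarkers. It then applies canonical correspondence or principal co-ordinates analysis, on which convex hulls may be drawn for each treatment and timepoint.

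Three hull quantities follow:

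- Overlaps between the hulls: "and the areas of overlap determined and compared".
- Each arm against its own screening hull: "the area of overlap from the follow up visits would be expressed as a percentage of screening".
- The arms against each other: "separately for each visit the convex hull area of GSK2245035 would be expressed relative to the Placebo convex hull area".

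The interpretation is that "The relative changes in these areas can potentially inform on magnitude and duration of treatment effects". The desired result is distinct clusters by arm together with "lasting changes (across FUV1, FUV2 and FUV3) in convex hull areas on active that are not observed on the placebo". The SAP gives no expected direction for the area change, no threshold, no adjustment for number of subjects, no measure of distance between group centres and no reference distribution. Outputs are scheduled as Table 5.28, Figure 5.71 and Listing 101 (SAP 11.13).

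**The concern.** A hull is fixed by its outermost points. Moving every point by the same amount moves the hull and leaves its area as it was. Removing points can only shrink it. The area ratio, and the hull-area half of the desired outcome, therefore respond to how scattered the subjects are and how many there are, not to how far treatment has moved them.

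Unequal numbers are foreseeable. Protocol 4.3 secures 20 completers per arm only through the one-week follow-up challenge. SAP 8.4.2.1.1 expects many subjects to lack evaluable sputum. SAP 8.4.3.3 also fills missing covariates with the arm mean at first, which pulls points inward.

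At stake is the reading of a reported output: an area change could be taken as evidence of a large or lasting effect, or its absence as evidence of none.

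**Working it through.** The documents give no figure for hull areas, so there is no planned value to reproduce. The check uses exact geometry and then simulation.

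**Inputs.** From the documents: 20 completers per arm (Protocol 4.3) and 18% and 27% attenuation as benchmark effects for minimum and weighted mean LAR (SAP 3.1). Assumed: normal scores, two axes, within-subject correlation 0.5, shifts of 0.5 to 2 SD, and the active arm reduced to 16, 14 or 12. Two versions were run: (a) bivariate normal scores, and (b) ten correlated variables, standardised and reduced jointly to two axes by Euclidean principal co-ordinates. There were 1,500 runs per scenario.

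**Shift.** For hull vertices (x_i, y_i), area = ½|Σ(x_i·y_{i+1} − x_{i+1}·y_i)|. Adding a constant to every point cancels. A numerical example gave 10.021 before and 10.021 after. On a log scale, a common fold change is such a constant.

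**Subject count.** The mean hull area of n bivariate normal points (4,000 runs) is 8.69 for n=20, 7.58 for n=16, 6.88 for n=14 and 6.24 for n=12. Relative to n=20: 7.58/8.69 = 0.87, 6.88/8.69 = 0.79 and 6.24/8.69 = 0.72, with no treatment effect.

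**Proportional attenuation.** If both axes shrink by 18%, area scales by 0.82² = 0.67. At 27% it would be 0.73² = 0.53.

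**Simulated medians (area ratio) and means (overlap), version (a) / version (b):**

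| Scenario | Active/placebo area ratio | Active overlap with own screening hull |
|---|---|---|
| No effect, 20 v 20 | 0.99 / 0.99 | 74% / 75% |
| Uniform 0.5 SD shift | 1.00 / 0.99 | 70% / 69% |
| Uniform 1 SD shift | 1.01 / 1.01 | 58% / 34% |
| Uniform 2 SD shift | 1.00 / 1.02 | 27% / 0% |
| No effect, 16 v 20 | 0.86 / 0.88 | 68% / 68% |
| No effect, 14 v 20 | 0.79 / 0.80 | 63% / 64% |
| No effect, 12 v 20 | 0.71 / 0.70 | 59% / 59% |
| Scores shrunk by 18% | 0.68 / 0.67 | 60% / 59% |

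Placebo overlap was 74–75% throughout.

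**Chance variation.** With no effect and 20 per arm, the area ratio has a 95% range of 0.49 to 2.08 in (a) and 0.47 to 2.03 in (b), and lies outside 0.8 to 1.25 in about 54% of trials. Its central 80% range in (a) is 0.64 to 1.55, so even 0.67 is unremarkable. Judged at a 5% level purely as a yardstick, a 1 SD shift is flagged in 5% of trials by the area ratio and in about 81% by the distance between centroids.

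**Lasting change.** The SAP sets no threshold. Suppose area must change from screening in the same direction at all three follow-up visits on active and not on placebo. With no effect, this occurs in roughly 10% of trials if the change must fall outside 0.8 to 1.25, and in a little over 20% if a change of about 10% suffices.

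**Overlap.** It moves with a shift, but losing four subjects (68%) looks much like a real 0.5 SD shift (69–70%). The between-arm difference in overlap has an SD of 18–20 points under no change.

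**The case against.** The strongest reply is that the plan does not rest on area alone. Overlap with screening, overlap between groups, distinct clusters by arm and, in the profile regression, a lower expected response in active clusters all depend on location. A reader might infer that a uniform benefit would go unseen; the documents do not support that, and the overlap column shows why. The sentence on magnitude and duration follows both the overlap and the ratio sentences, and the wish for lasting changes on active could be meant as screening-referenced overlap. This stands, and it confines the point to the area ratio and to hull area read literally. Placebo also supplies a null level for overlap, although not its sampling variation or a correction for unequal numbers.

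Three other strong readings also fail:

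- That any benefit leaves the area unchanged. A proportional attenuation of untransformed endpoints does shrink it.
- That dropout alone reproduces the whole desired result. Random dropout would not be expected to create distinct clusters by arm.
- That half the subjects improving and half worsening would be a false signal. The area ratio does rise (1.42 in version (a) and 2.24 in version (b) for ±1 SD), but if the drug causes this it is a real effect with zero mean.

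The analysis is also exploratory, open to refinement and may not be attempted. Protocol 9.1 plans no formal tests, and treatment differences by visit are estimated in the repeated-measures models (SAP 8.1.2 and 8.4.2). That limits the consequence but does not make area a measure of effect size. Canonical correspondence analysis was not simulated.

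**Conclusion.** The point holds in a limited form. The active/placebo hull-area ratio and the hull-area half of the desired outcome describe spread and subject count. They stay at about 1 under a uniform additive shift and fall to about 0.87 and 0.80 when one arm has 16 or 14 subjects against 20. By chance alone they range over about 0.5 to 2.1. An 18% proportional attenuation moves the ratio only to about 0.67, inside that range. These sizes rest on normal scores on two axes; the invariance to an additive shift on fixed axes is exact. The location-sensitive parts of the plan remain useful, but overlap needs a reference distribution and is itself affected by numbers. This is a low-cost improvement to an exploratory output, not a threat to the trial's conclusions.

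**What to change.** In SAP 8.4.3.3, add the distance between arm centroids of the change-from-screening ordination scores at FUV1, FUV2 and FUV3 as the measure of magnitude and duration. Refer it to a permutation distribution that reallocates arm labels between subjects within the randomisation strata (centre and allergen exposure, Protocol 6.2) and keeps each subject's visits together. Six planned centres and two exposure levels give 12 cells, about 40/12 = 3.3 completers each, so sparse centres will need pooling; SAP 11.9.1 already says to pool within country first.

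Keep hull areas as a description of spread, compared at equal numbers of subjects (for example by resampling the larger arm), and state the direction of change expected. Quote overlap against the same permutation reference.

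The cost is a few lines of SAP text and a short permutation step in an exploratory analysis.
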